Because patients sustaining femoral neck fractures rarely undergo surgical intervention in the same day, they are typically given a dose of either enoxaparin or heparin upon admission to prevent deep vein thrombosis given their injury and immobility. Patients receive this medication each day until the day of their surgical intervention, at which time this medication is held to prevent excessive intra-operative blood loss. The drug is resumed on post-operative day 1 for deep vein thrombosis prophylaxis. The drug insert for enoxaparin states, “significant anti-factor Xa activity persists for 12 hours following a 40 mg subcutaneous once a day dosing.” Because this medication is held on the day of surgery, there is greater than 12 hours from the last dose received until the surgical intervention. Patients who receive either enoxaparin or heparin will be included in the study. We will record the use of these medications (e.g. enoxaparin and heparin) and the interval between the last dose of medication and the surgical intervention for covariate analysis. Given how common the in-hospital use of these medications is in patients prior to undergoing hip hemiarthroplasty, we expect to achieve balanced groups through the process of randomization. Coagulation labs (PT/PTT/INR), when obtained prior to surgery, will be recorded to demonstrate similarity between the groups.

➤ *Describe length of subject’s participation in the study including number of visits, frequency of visits, and length of visits:*

Patients will be in the study for 4 to 6 weeks. This time period will encompass their inpatient hospital stay and their first two outpatient visits (one at approximately 2 weeks, a second at 4-6 weeks). These visits are the regularly scheduled post-operative visits that are part of routine care follow up. No extra time per visit or number of visits will be required as a result of study inclusion. The scheduled date of the patient’s post-operative outpatient visit occurring between 4 and 6 weeks will reflect the last day of study involvement.

➤ *Methods of Data Collection and Types of Data to be collected:*

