All data will be collected using an IRB approved data collection form. Data will consist of demographic information (age, gender, body mass index, injury side, comorbidities, etc.), pre- and postoperative blood values (hematocrit/hemoglobin, PT/PTT/INR (if obtained), etc.), pre-operative anti-platelet use (aspirin, etc.), pre-operative heparin or enoxaparin use and interval between last dose and the surgical procedure, time from admission to surgical intervention, intra-

operative details (approach, cemented vs. un-cemented, surgeon, operative time, anesthesia, and estimated blood loss), packed red blood cell transfusion rates and amount, length of inpatient stay, prescribed chemoprophylaxis, complications (transfusion related complications, deep vein thrombosis, pulmonary embolism, myocardial infarction, stroke, death, infection, hematoma), and inpatient cost. Detailed list of the data to be collected as well as time points of collection can be found in the attachment to this labeled “Data Collection Forms.”

The primary outcome measure is the rate of packed red blood cell transfusion. Secondary outcome measures include amount of packed red blood cell transfusion, difference between pre- and postoperative hemoglobin/hematocrit, length of stay, complications, and inpatient cost.

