transfusion, will be analyzed using a two-group continuity corrected Chi-square test. Differences in packed red blood cell transfusion rates, amount of blood transfused, and inpatient cost will be analyzed using a two-group *t* test. Regression analysis will be used to model packed red blood cell transfusion outcomes against the main predictors (group allocation), adjusting for the effect of covariates (comorbidities, post-operative venous thromboembolism prophylaxis, etc.). Specifically, logistic regression will be used to model packed red blood cell transfusion as a binary outcome (yes or no) and multiple linear regression will be used to model packed red blood cell transfusion amounts and rates. The alpha level for all statistics will be set at 0.05.

5. Timetable

- Expected Start Date: 11/1/15
- General Time Table: 2 years
- Expected Completion Date: 10/31/17

6. Budget / resources:

We have received a Resident Research Project grant award from the Orthopaedic Research and Education Foundation (OREF). The pharmacy, which will play an essential role in this project, has been appropriately budgeted and is available to participate in this study.

7. Dissemination

We plan to disseminate the results of our research in the form of a peer reviewed journal article as well as application for presentation at a national society meetings.

8. References / Literature Review:

Topical (Intra-Articular) Tranexamic Acid and Transfusion Rates Following Hip Hemiarthroplasty

2. Eubanks JD. Antifibrinolytics in Major Orthopaedic Surgery (Review). *J Am Acad Orthop Surg.* 2010;18(3):132-8.

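### The hemoglobin/hematocrit outcome has no stated analysis; prespecifying adjustment for the preoperative value would generally gain precision and needs no new data

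*Combined protocol and SAP*

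**What the plan says.** All references are to section 4 of the combined protocol and SAP.

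- **Outcome.** Under Methods of Data Collection and Types of Data to be collected, the secondary outcomes include the "difference between pre- and postoperative hemoglobin/hematocrit". The same paragraph collects "pre- and postoperative blood values (hematocrit/hemoglobin, PT/PTT/INR (if obtained), etc", so the preoperative value will be in the dataset. Collection time points are left to an attached form that is not part of the documents.
- **Simple comparisons.** Under Method(s) of data analysis, the sentence that assigns the *t* test reads: "Differences in packed red blood cell transfusion rates, amount of blood transfused, and inpatient cost will be analyzed using a two-group". Hemoglobin and hematocrit are not in that list.
- **Adjusted analyses.** The same paragraph opens its modelling plan with "Regression analysis will be used to model packed red blood cell transfusion outcomes against the main predictors (group allocation". Covariates there are given by example only: "adjusting for the effect of covariates (comorbidities, post-operative venous thromboembolism prophylaxis, etc". Logistic regression handles transfusion as a binary outcome; for the continuous models, "multiple linear regression will be used to model packed red blood cell transfusion amounts and rates". Again hemoglobin is not among the modelled outcomes.
- **Covariates.** Besides comorbidities and thromboembolism prophylaxis, the text under Exclusion criteria names anti-platelet drugs and the use and timing of heparin or enoxaparin. Preoperative hemoglobin is not named as a covariate anywhere.
- **Other laboratory values.** Preoperative coagulation results "will be recorded to demonstrate similarity between the groups". Hemoglobin/hematocrit is therefore the only laboratory measure among the listed outcomes.

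**The concern.** The only operation that the plan specifies for hemoglobin is subtraction. With no test named and regression reserved for transfusion, an analyst following the text would most naturally compare mean change between arms without adjustment. A change score fixes the slope of the postoperative on the preoperative value at 1. Baseline adjustment estimates that slope from the data. Where the true slope differs from 1, the change score carries avoidable variance, and part of any chance baseline difference between two arms of about 51 shows up in the estimated effect.

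The stake is precision on the one listed outcome that reads the drug's effect from a laboratory value. The trial is sized only for a large transfusion difference (35% against 10%), so hemoglobin would be important supporting evidence if the true difference is smaller. Leaving the method open also allows the choice between raw change and an adjusted analysis to be made after the data are seen.

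**Working it through.** **Inputs.** From Sample size and justification: 35% against 10%, two-sided 0.05, 80% power, continuity-corrected chi-square, 51 per arm (102 total). From Method(s) of data analysis: "The alpha level for all statistics will be set at 0.05". Not in the documents, hence assumed: the SDs before and after surgery (s_pre, s_post) and their correlation r.

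**1. The plan's own figure.** With mean proportion 0.225, the uncorrected size is

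n = [1.960 × √(2 × 0.225 × 0.775) + 0.842 × √(0.35 × 0.65 + 0.10 × 0.90)]² / 0.25² = 42.6, or 43 per arm.

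The continuity correction, (n/4) × [1 + √(1 + 4/(n × 0.25))]², gives 50.3, or 51 per arm, as stated; corrected power at 51 is 80.7%. This concerns the primary outcome only. The plan gives no figure for hemoglobin.

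**2. Two analyses of hemoglobin.** Per-patient variance behind the treatment contrast:

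- change score: s_pre² + s_post² − 2·r·s_pre·s_post
- adjusted for the preoperative value: s_post²·(1 − r²)

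The first minus the second is (s_pre − r·s_post)² = s_pre²·(1 − β)², where β = r·s_post/s_pre is the slope. It is never negative, and it is zero only when β = 1. Adjustment costs about one degree of freedom (99 residual instead of 100).

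**3. Equal SDs.** The variance ratio, adjusted over change, is (1 − r²)/[2(1 − r)] = (1 + r)/2. The equivalent number of patients is 102 divided by the ratio. Power is for an effect that raw change would detect with 80% power at 51 per arm: Φ(2.802/√ratio − 1.960).

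| r | Variance ratio | Variance reduction | CI narrower by | 102 patients worth about | Power if 80% by change |
|---|---|---|---|---|---|
| 0.3 | 0.65 | 35% | 19% | 157 | 93.5% |
| 0.5 | 0.75 | 25% | 13% | 136 | 89.9% |
| 0.7 | 0.85 | 15% | 8% | 120 | 86.0% |
| 0.8 | 0.90 | 10% | 5% | 113 | 84.0% |
| 0.9 | 0.95 | 5% | 2.5% | 107 | 82.0% |

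A simulation of 5,000 trials per r, with 51 per arm, gave ratios of 0.65, 0.76, 0.84 and 0.95 at r = 0.3, 0.5, 0.7 and 0.9.

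**4. Unequal SDs.** Variance ratio at the same values of r:

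| s_post/s_pre | r = 0.3 | 0.5 | 0.7 | 0.8 | 0.9 |
|---|---|---|---|---|---|
| 0.8 | 0.50 | 0.57 | 0.63 | 0.64 | 0.61 |
| 1.25 | 0.78 | 0.89 | 0.98 | 1.00 | 0.95 |

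At a ratio of 1.25 and r = 0.8 the slope is 1.25 × 0.8 = 1 and nothing is gained.

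**5. Chance baseline imbalance.** If the arms differ by D at baseline, the change-score contrast shifts by (β − 1)·D. With equal SDs and r = 0.7 that is −0.3·D. A one-standard-error imbalance is s × √(2/51) = 0.198·s, so the shift is about 0.06·s in the opposite direction (0.3 × 0.198 = 0.059).

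**6. Change or postoperative value.** Once the preoperative value is a covariate, modelling the change and modelling the postoperative value give the same treatment estimate. Defining the outcome as a difference therefore loses nothing by itself.

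**The case against.** **The plan is silent; it has not chosen an unadjusted test.** This stands. A reader might infer that the plan prescribes a raw comparison. It does not: it names the outcome and gives no analysis. The unadjusted reading is an inference from the outcome's definition and from the scope of the regression sentences. The open-ended covariate list does not rescue it, because that list sits inside models for transfusion.

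**The comparison is not biased.** This also stands. A reader might infer that a baseline difference between arms passes in full into the estimate. It would do so only with a slope of 0; otherwise the carry-over is (slope − 1) times the difference. Randomisation keeps the change-score comparison unbiased on average, so the issue is precision and chance imbalance.

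**The slope is not known to be below 1.** The documents give neither r nor SDs. Surgery is rarely on the day of injury, and transfusing patients who start low would flatten the slope. Both make a slope below 1 plausible, but the text does not show it. Nor does anything in the documents support taking the r = 0.3 row as the expected gain.

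**Transfusion itself raises postoperative hemoglobin.** With 35% and 10% assumed to be transfused, this could mask a difference between arms, and baseline adjustment does not cure it. That limits what the outcome can show. It is no reason to leave the analysis unspecified or less precise.

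**The outcome is secondary.** It carries no power claim, so this remains an efficiency point.

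**Conclusion.** The point holds as an improvement that needs no new data, confined to one secondary outcome. The plan defines a pre/post difference in hemoglobin/hematocrit, assigns it no test and limits adjustment to transfusion outcomes. Read naturally, that leaves an unadjusted comparison of change scores. Adjusting for the preoperative value is at least as precise, apart from about one degree of freedom.

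The size of the gain rests on assumed values. With equal SDs, the variance falls by 35% at r = 0.3 and by 5% at r = 0.9; for r between 0.5 and 0.8 it falls by 25% to 10%. With unequal SDs the gain can be larger or can vanish. The documents do not support a claim of bias, of a deliberate unadjusted choice, or of any particular gain. The primary test, the 51 per arm and the stated power are unaffected.

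**What to change.** Add to Method(s) of data analysis: postoperative hemoglobin, and separately hematocrit (or equivalently the change in each), will be analysed by linear regression on allocated group with the corresponding preoperative value as covariate; the adjusted mean difference will be reported with its 95% CI. Define the preoperative value as the last one before incision, or as the preoperative time point already set in the Data Collection Forms.

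The cost is one or two sentences. The values are already collected, and no extra patients or visits are needed. The treatment of hemoglobin values measured after a transfusion should be settled separately.

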Following surgery, the patient will be admitted to the hospital per the standard of care. The length of inpatient stay following this procedure is approximately 3 to 4 days, however this may vary. Following discharge from the hospital, patients will follow up with the treating surgeon at two outpatient visits (one at approximately 2 weeks, a second at 4-6 weeks). These visits are the regularly scheduled post-operative visits as part of routine care. The methods and types of data to be collected are described in the “Methods of Data Collection” section of this protocol.

➤ *Sample size and justification:*

A sample size calculation was conducted to determine the number of patients needed to observe a difference in packed red blood cell transfusion rates. In the last two fiscal years at UCHC a hip hemiarthroplasty has been performed in 84 patients, 29 of which required packed red blood cell transfusions (34.5%). We queried the Health Care Utilization Project Database, a stratified 20% national sample of over 7,000,000 hospital stays at over 1,000 hospitals in 46 states, to estimate national rates of packed red blood cell transfusion. In this sample, 14,813 of 45,800 (32.3%) patients undergoing hip hemiarthroplasty in 2011 required a packed red blood cell transfusion. Given these numbers, we used a value for packed red blood cell transfusion rate of 35% for patients that receive placebo. The literature has shown packed red blood cell transfusion rates with use of the drug in an orthopedic setting in similar populations to range from 12.5% to 1%. Accordingly, we selected a packed red blood cell transfusion rate of 10% in patients receiving tranexamic acid. A two group continuity corrected Chi square test with a 0.05 two-sided significance level will have 80% power to detect the difference between packed red blood cell

Topical (*Intra-Articular*) Tranexamic Acid and Transfusion Rates Following Hip ~~Hemiarthroplasty~~

transfusion rates of 35% and 10% (odds ratio of 4.846) when the sample size in each group is 51 (102 total).

➤ *Explain on what basis it is reasonable to assume that the sample size will be obtained:*

The number of hip hemiarthroplasties performed annually has been increasing. In the last fiscal year, 49 hip hemiarthroplasties were performed at UCHC. With a 2-year study period and the possibility that the study may be extended to neighboring facilities (St. Francis Medical Center), it is reasonable to assume the sample size will be obtained.

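### The continuity-corrected chi-square for the primary outcome meets its planned power, but Boschloo's exact test would give about 5 points more (86.4% against 81.6%) from the same 102 patients within the 5% bound

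*Combined protocol and SAP*

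**What the plan says.** In section 4 of the combined protocol and SAP, under the data collection heading: "The primary outcome measure is the rate of packed red blood cell transfusion". Under the data analysis heading, that outcome's comparison, in the document's words, "transfusion, will be analyzed using a two-group continuity corrected Chi-square test". The same paragraph closes with "The alpha level for all statistics will be set at 0.05".

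The sample size paragraph rests on the same test: "A two group continuity corrected Chi square test with a 0.05 two-sided significance level will have 80% power". Its rates are set by "we used a value for packed red blood cell transfusion rate of 35% for patients that receive placebo" and "we selected a packed red blood cell transfusion rate of 10% in patients receiving tranexamic acid", and the result is 51 per arm, 102 in total, with an odds ratio of 4.846.

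Sizing and analysis therefore agree. The document gives no reason for the continuity correction and does not mention the error rate that the corrected test actually has at this sample size.

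**The concern.** With two arms of 51 and a yes/no outcome, the continuity correction pulls the chi-square statistic towards zero. The test then rejects less often under no effect than the nominal 5% allows, and less often under a real effect than other tests that also keep to 5%. If a valid test can reject more tables without breaching the bound, the planned test leaves unused some of the information that the 102 patients provide. A real reduction in transfusion would then be somewhat more likely to be reported as non-significant. What is at stake is efficiency, not validity.

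**Working it through.** **Inputs.** All come from section 4, sample size paragraph, unless noted: placebo 35%, tranexamic acid 10%, two-sided 0.05, 80% power, 51 per arm with equal allocation. For sensitivity, the national rate of 32.3% replaces 35%, or 12.5%, the upper end of the quoted treated range, replaces 10%. Section 2 also cites a hemiarthroplasty transfusion rate of 46.6%. The document makes no allowance for dropout, so none is assumed here.

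**Step 1: reproduce the plan's figure.** The mean rate is (0.35 + 0.10)/2 = 0.225 and the difference is 0.25.

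- Without correction: n' = [1.960·√(2·0.225·0.775) + 0.842·√(0.35·0.65 + 0.10·0.90)]² / 0.25² = (1.157 + 0.474)²/0.0625 = 42.6, so 43 per arm.
- With correction: n = (n'/4)·[1 + √(1 + 4/(n'·0.25))]² = 50.3, so 51 per arm. This matches the plan.
- Odds ratio: (0.35/0.65)/(0.10/0.90) = 4.846. This matches too.

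**Step 2: exact error rate and power.** Let *a* and *b* be the numbers transfused in the two arms and *m* = *a* + *b*. The corrected statistic is

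102·(|a(51−b) − b(51−a)| − 51)² / [51²·m·(102−m)],

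with the bracket set to zero if negative, and the test rejects at 3.841 or more. For each test, the probability of rejection is the sum of Bin(a; 51, p₁)·Bin(b; 51, p₂) over the rejected tables among all 52 × 52. Equal rates give the type I error, and unequal rates give the power. Boschloo's test orders tables by the two-sided Fisher p-value and takes the largest cut-off that keeps the maximum error over all common rates at or below 5%. At 51 per arm that cut-off is 0.0696.

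Exact two-sided type I error:

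| Common rate | Corrected | Boschloo | Uncorrected |
|---|---|---|---|
| 10% | 1.8% | 3.2% | 4.9% |
| 22.5% | 2.6% | 4.2% | 5.1% |
| 35% | 3.0% | 4.7% | 5.1% |
| 46.6% | 3.7% | 4.1% | 5.9% |
| Maximum over all rates | 3.7% | 4.8% | 5.9% |

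Exact power at 51 per arm:

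| True rates | Corrected | Boschloo | Uncorrected |
|---|---|---|---|
| 35% v 10% | 81.6% | 86.4% | 88.1% |
| 35% v 12.5% | 69.5% | 75.6% | 78.3% |
| 32.3% v 10% | 72.6% | 78.9% | 81.2% |

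The gain from Boschloo's test is 86.4 − 81.6 = 4.8 points at the design rates, and 6.1 and 6.3 points in the other two rows.

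**Step 3: compare the rejection regions.** At 51 per arm Boschloo's test rejects every table that the corrected test rejects, and 60 more. One of the 60 is 17/51 against 8/51. Its corrected statistic is 102·(459 − 51)²/(51²·25·77) = 3.39, below 3.841. Its Fisher p-value is 0.064, below the cut-off of 0.0696, so Boschloo's test rejects.

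**The case against.** The strongest reply is that the plan is sound as written. The trial was sized on the test it will use, the planned power is met, and the larger sample (51 rather than 43 per arm) already pays for the correction. That stands in full. Power is lost only relative to another test, not relative to what the plan promises.

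It can also be said that conservatism with discrete data is ordinary. Fisher's exact test, a routine choice, has 83.1% power here and an error rate of 1.8% to 3.1% over common rates of 10% to 35%. That stands too, and it is why this is a suggestion and not a criticism of an unusual method. It does not remove the gain, because Boschloo's test also guarantees the 5% bound.

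Three stronger readings are tempting, and the documents do not support them:

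- *The test fails to run at the stated 5%.* The 0.05 in the analysis paragraph is a nominal threshold, in effect a ceiling, and the corrected test never goes above 3.7%.
- *Dropping the correction gains more than 6 points.* The uncorrected chi-square does gain 88.1 − 81.6 = 6.5 points, but partly by exceeding 5%. The excess is not confined to extreme rates. It is 0.1 point at the plan's own 35% and 0.9 point at the 46.6% the document cites.
- *The trial could shrink to 43 per arm.* The uncorrected test has 82.7% power there at 35% v 10%, but with no allowance for dropout and with the treated rate at its assumed 10%. At 12.5%, even 51 per arm with Boschloo's test gives only 75.6%.

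**Conclusion.** This is a worthwhile, low-cost improvement, and no figure in the plan is wrong. With a strict 5% bound the gain is about 5 points of power at the design rates and about 6 points if the placebo rate is 32.3% or the treated rate 12.5%. The results assume 51 analysed patients in each arm, independent binary outcomes and no dropout. The description of the error rate as 1.8% to 3.0% holds for common rates of 10% to 35%, and outside that range it differs. The enumeration is exact, so the remaining uncertainty lies in the true transfusion rates and the final arm sizes.

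**What to change.** In the data analysis paragraph, name Boschloo's unconditional exact test, two-sided at 0.05, as the single primary test of the transfusion rate, and report the risk difference with a 95% score interval. In the sample size paragraph, keep 102 patients and restate power as about 86% at 35% v 10%. If the arms do not finish at 51 each, the test is recomputed for the actual sizes.

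The cost is two edited sentences and no extra patients or data, with three things to accept:

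- The test is less familiar to readers and needs a named software routine.
- A score interval is tied to the uncorrected statistic, so it can exclude zero in a few tables where Boschloo's test does not reject. The plan should say that the test decides.
- The change must be documented and made by people blind to outcomes by arm. The document does not state how far enrolment has gone. Its page header carries a 2018 date, later than the expected completion date of 10/31/17. Appendix A provides for unblinding at adverse events and for unblinded review by the monitoring board. If an unblinded outcome comparison has already been made, keep the corrected test as primary and report Boschloo's test as a sensitivity analysis.

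### The primary transfusion test is unadjusted and preoperative hemoglobin, already collected, is nowhere named as a covariate: prespecifying it is a free efficiency gain, not the repair of an error

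*Combined protocol and SAP*

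**What the plan says.** Section 4, Methods of Data Collection: "The primary outcome measure is the rate of packed red blood cell transfusion". The same section lists "pre- and postoperative blood values (hematocrit/hemoglobin, PT/PTT/INR (if obtained), etc" among the data collected; the qualifier in that list attaches to the coagulation tests, not to hemoglobin. The change in hemoglobin/hematocrit from before to after surgery is a secondary outcome, so the plan already needs the baseline value.

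Section 4, Method(s) of data analysis: the primary outcome "will be analyzed using a two-group continuity corrected Chi-square test". The same paragraph plans a logistic regression of transfusion on group, "adjusting for the effect of covariates (comorbidities, post-operative venous thromboembolism prophylaxis, etc". That model is not called primary and its covariate list is left open. The Exclusion criteria text adds antiplatelet use, and heparin or enoxaparin use with the interval since the last dose. Hemoglobin is not named in any of these places.

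Section 4, Sample size and justification: "we used a value for packed red blood cell transfusion rate of 35% for patients that receive placebo" and "we selected a packed red blood cell transfusion rate of 10% in patients receiving tranexamic acid"; the corrected chi-square "with a 0.05 two-sided significance level will have 80% power" with 51 per group.

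Section 4, Study Procedures: allocation is in blocks, and no stratification factor is named. The pharmacy opens the envelope once the patient reaches the operating room, so a preoperative hemoglobin cannot be affected by allocation.

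**The concern.** Red cells are given for low hemoglobin, so the starting value plausibly predicts who is transfused. If it does, a crude two-by-two comparison leaves explainable variation in the error term. The trial expects only 51 × 0.35 + 51 × 0.10 = 22.95, about 23, transfused patients, so precision is scarce. Without stratification, a chance difference in baseline hemoglobin between arms would also feed into the crude difference, and the primary analysis has no means of removing it. If hemoglobin is added to the supportive model only after an imbalance is seen, that adjusted result is post hoc.

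**Working it through.** **1. The plan's own figure.** Inputs from Sample size and justification: p₁ = 0.35, p₂ = 0.10, d = 0.25, mean rate 0.225, two-sided α = 0.05, power 80%.

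- Uncorrected: n′ = [1.960 √(2 × 0.225 × 0.775) + 0.842 √(0.35 × 0.65 + 0.10 × 0.90)]² / 0.25² = (1.157 + 0.474)² / 0.0625 ≈ 42.6, i.e. 43 per group.
- Corrected: n = (n′/4) [1 + √(1 + 4/(n′d))]² = 10.65 × (1 + 1.173)² ≈ 50.3, i.e. 51 per group, as stated.
- Exact binomial power at 51 per group: 81.6% corrected, 88.1% uncorrected.

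**2. Power with and without hemoglobin.** Simulation with 51 per arm and 4,000 trials per scenario. Hemoglobin is standard normal, and intercepts are solved so that the marginal rates stay at 35% and 10%. ASSUMPTION: the odds ratio (OR) for transfusion per SD of hemoglobin, because the documents give none. The adjusted test is the likelihood-ratio test for group in a logistic model with group and hemoglobin.

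| OR per SD | Planned (corrected) | Unadjusted, uncorrected | Adjusted |
|---|---|---|---|
| 1 (none) | 81-82% | 88-89% | 88.8% |
| 1.5 | 81-82% | 88-89% | 89.5% |
| 2 | 81-82% | 88-89% | 90.7% |
| 3 | 81-82% | 88-89% | 92.9% |
| 4 | 81-82% | 88-89% | 94.2% |

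The first two tests do not use hemoglobin, so their power does not depend on the OR; over all scenarios they ran 81.4-82.0% and 87.9-88.6%. The step from the planned test to the uncorrected one, 6 to 7 points, has nothing to do with hemoglobin. The step from uncorrected to adjusted is hemoglobin's share: about 2 to 5 points at OR 2 to 3. A separate 5,000-trial simulation agrees: 88.5% to 88.9% at OR 1, 88.3% to 89.7% at 1.65, and 88.9% to 93.1% at 2.7.

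The ratio of unadjusted to adjusted variance of the risk difference is 1.06 at OR 2 and 1.14 at OR 3. That is like analyzing 102 × 1.06 ≈ 108 to 102 × 1.14 ≈ 116 patients without adjustment.

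**3. A smaller effect.** The topical total-hip trial in the background section went from 32.1% to 12.5%, a ratio of 0.39. Applied to 35% this gives 0.39 × 35% = 13.65%. At 35% v 13.65%, power is about 63-65% for the planned test, 73-74% uncorrected and 77-82% adjusted at OR 2 to 3. Hemoglobin's share is about 4 to 8 points.

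**4. Type I error.** With 22.5% in both arms: corrected chi-square 2.3-2.8%; adjusted likelihood-ratio test 5.0-5.9%; adjusted Wald test 4.2-4.9%.

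**5. Chance imbalance.** The standard error of the between-arm gap in mean hemoglobin is √(2/51) = 0.198 SD. P(gap above 0.4 SD in either direction) = 2[1 − Φ(0.4/0.198)] = 4.3%. To get the shift, move each arm's hemoglobin distribution by half the gap in opposite directions and recompute both marginal rates:

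| Gap | Rates | Shift at OR 2 | Shift at OR 3 |
|---|---|---|---|
| 0.2 SD | 35% v 10% | 2.0 points | 2.9 points |
| 0.4 SD | 35% v 10% | 4.0 points | 5.8 points |
| 0.4 SD | 35% in both arms | 5.7 points | 8.1 points |

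The middle row is the one to set against the planned 25-point effect, because it uses the plan's own rates.

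**The case against.** The strongest reply is that nothing is broken. Design and analysis use the same test, the sample size reproduces, randomization keeps the type I error below 5%, and an unadjusted primary test with an adjusted supportive model is a conventional plan. All of this stands. The supportive logistic model also covers the same outcome, and its list does not exclude hemoglobin. What remains is that hemoglobin is not prespecified anywhere and that no adjusted analysis is primary.

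Three stronger readings are tempting and not supported:

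- A reader might infer that hemoglobin adjustment lifts power by about ten points, from 82% to 91-93%. Most of that gap is the continuity correction. It is obtained by moving from a test with a size of 2-3% to one whose simulated size is about 5-6%.
- A reader might take a shift of 6 to 8 points from a 0.4 SD imbalance. That needs a 35% rate in both arms, and so does not belong beside a 25-point effect. The crude standard error already includes such variation on average; the exposure is conditional on the allocation obtained.
- A reader might take "we expect to achieve balanced groups through the process of randomization" as the plan's general reliance on balance. In its place, the Exclusion criteria text, it concerns only in-hospital enoxaparin and heparin.

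The premise that hemoglobin is strongly prognostic is also not in the documents. They state no hemoglobin trigger, and the background section links the transfusion threshold to age and comorbidity. This limits confidence in the size of the gain, but not the recommendation, since adjustment loses no power at OR 1.

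**Conclusion.** The point holds as an efficiency improvement. The primary test is valid and meets its 80% target, but it leaves unused a baseline value that the trial already collects. Under an assumed odds ratio of 2 to 3 per SD, prespecified adjustment is worth about 2 to 5 points of power at the design rates and about 4 to 8 points at 35% v 13.65%. It also removes most of a possible 4 to 6 point shift from a 1-in-20 imbalance. The gain is under 2 points at an odds ratio of 1.5 and nil at 1. The direction is secure; the size rests on that assumption. No dropout was applied, because the plan gives no rate.

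**What to change.** In Method(s) of data analysis, define the primary analysis as a logistic regression of transfusion (yes/no) on randomized group and the last preoperative hemoglobin, entered as a continuous variable. Test group by likelihood ratio at two-sided 0.05. Report the risk difference standardized over the observed hemoglobin values, with a 95% CI. The risk difference is needed because the adjusted odds ratio is not the design's 4.846: at an odds ratio of 2.7 per SD, the same marginal rates correspond to a conditional odds ratio of 6.16.

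Keep the corrected chi-square as the supportive unadjusted analysis, and note that the likelihood-ratio test ran at 5.0-5.9% in simulation. With about 23 events, limit the primary model to these two terms. Postoperative prophylaxis in particular is chosen after randomization and should not enter it.

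Cost: one paragraph of wording, with no new data, no extra patients and no change to the sample size.
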